2.2 Study Objectives

Primary Objectives:

- 1) *Among patients with HR+/HER2- A/MBC receiving palbociclib combination therapy with AI as first-line therapy:*
 - a. *Describe demographic and clinical characteristics.*
 - *Demographic characteristics will include age, sex, race, insurance status, menopausal status, and region of residence at A/MBC diagnosis.*

[figure not shown]
PFIZER CONFIDENTIAL

- *Clinical characteristics will include variables such as, stage of initial diagnosis, histology, Eastern Cooperative Oncology Group (ECOG) performance status (where ECOG score unavailable, Karnofsky performance status will be converted to corresponding ECOG score) and comorbid disease burden utilizing the Charlson Comorbidity Index, HER2 and estrogen receptor (ER)/ progesterone receptor (PR) status, BRCA status, number and sites of distant metastasis at A/MBC diagnosis (visceral (defined as liver, lung, peritoneum, and pleural nodules), non-visceral, bone only); modalities of treatment received prior to A/MBC diagnosis (chemotherapy, hormone therapy, surgery, radiation therapy) documentation of endocrine sensitivity and endocrine resistance if hormone therapy was received in the adjuvant setting, time to metastasis (time between initial and metastatic diagnosis) and disease free interval (time between completion of adjuvant therapy and diagnosis of A/MBC).*
- b. *Describe treatment patterns.*
 - *Distribution of regimens from the diagnosis of A/MBC through the end of the record.*
 - *Sequence of regimens across lines, through the end of the record of systemic therapy.*
 - *Description of the dosing will include the starting dose, end dose, dose adjustment (dose increase and dose reduction), type of dose adjustment (dose modification, schedule changes, dose delay, or hold) discontinuation, reason (including progression, end of planned therapy, insurance changes, schedule change, dose delay, hold, cost, patient refusal, toxicity), and time to dose adjustment (discontinuation).*
- 2) *Among patients receiving palbociclib + AI as first-line therapy, examine clinical effectiveness outcomes including:*
 - a. *Real-world progression-free survival (rwPFS) will be assessed for the first-line therapy.*
 - b. *Real-world overall survival (rwOS) will be assessed from the start of the first-line therapy.*
 - c. *Real-world time to next therapy (rwTTNT) will be assessed from the start of the first-line therapy.*

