4 ANALYSIS SETS/POPULATIONS

Analysis population will be all patients identified from the Syapse Learning Health Network database who meet the following inclusion and exclusion criteria-

Inclusion criteria

Patients must meet all of the following inclusion criteria to be eligible for inclusion in the study:

1. *Female or male sex.*
2. *Diagnosis (confirmed by clinical review) of A/MBC, defined as breast cancer at stage IIIB, stage IIIC, stage IV or identified as having distant metastasis.*
3. *Age ≥ 18 years at A/MBC diagnosis.*
4. *Initiated palbociclib in combination with an AI as first-line therapy after A/MBC diagnosis on or after 03 February 2015 through 31 July 2019. Note that the date of the start of the inclusion period reflects the month of palbociclib US FDA approval.*
5. *Evidence of ER or PR positive disease, or absence of any indication of ER and PR negative disease closest to A/MBC diagnosis (ie patients are eligible without affirmative indication of ER/PR+ status as long as ER/PR- indication is not present).*
6. *Evidence of HER2 negative disease, or absence of any indication of HER2 positive disease closest to A/MBC diagnosis (ie patients are eligible without affirmative indication of HER2- status as long as HER2+ indication is not present).*

Exclusion criteria

Patients meeting any of the following criteria will not be included in the study:

[figure not shown]
[figure not shown]
1. *Enrollment in an interventional clinical trial for A/MBC during the study observation period.*
2. *Evidence of prior treatment with any CDK4/6 inhibitor in the adjuvant setting (i.e. a CDK4/6 inhibitor is administered (start date) > 30 days prior to the A/MBC diagnosis date).*
3. *Evidence of another primary cancer within 3 years prior to the initial line containing palbociclib.*

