5 ENDPOINTS AND COVARIATES

Primary Endpoints-

1. To summarize the demographic and clinical characteristics.
Demographic characteristics will include

PFIZER CONFIDENTIAL

- Year of initial, metastatic and AMBC diagnoses;
- age at initial diagnosis, A/MBC diagnosis, start of palbociclib treatment and death;
- sex;
- race;
- ethnicity
- insurance status;
- menopausal status;
- region of residence at A/MBC diagnosis.

Clinical characteristics will include

[figure not shown]
- stage of initial diagnosis;
- histology;
- Eastern Cooperative Oncology Group (ECOG) performance status (where ECOG score unavailable, Karnofsky performance status will be converted to corresponding ECOG score);
- prior surgery (and type);
- prior radiation therapy (and type);
- comorbid disease burden (see Section 9.2);
- Charlson comorbidity index
- Sites of metastasis – visceral (liver, lung, peritoneum and pleural nodules), non-visceral, bone only
- Number of metastatic sites
 - Number of lesions in the site
 - Disease burden in the liver, lungs, bone
- time to metastasis (time between initial and metastatic diagnoses)
- HER2 and estrogen receptor (ER)/ progesterone receptor (PR) status;
- BRCA status
- modalities of treatment received prior to A/MBC diagnosis (chemotherapy, hormone therapy, surgery, radiation therapy);
 - Documentation of endocrine sensitivity and endocrine resistance if hormone therapy received in adjuvant setting
- disease free interval (time between completion of adjuvant therapy and diagnosis of A/MBC).

2. To summarize treatment patterns.

Treatment patterns will be evaluated by the review of

- the distribution of regimens;
- sequence of regimens across the lines;
- description of dosing which will include the starting dose, end dose, dose adjustment (dose increase and dose reduction), type of dose adjustment (dose modification, schedule changes, dose delay or hold), discontinuation reason (including death, progression, end of planned therapy, insurance changes, schedule change, dose delay, hold, cost, patient refusal, toxicity), and time to dose adjustment

PFIZER CONFIDENTIAL

[figure not shown]

3. To summarize the effectiveness outcomes of treatment-
 - a. Real-world progression-free survival (rwPFS) for the first-line therapy at time points 3, 6, 12, 18, 24, 30, and 36 months;
 - b. Real-world overall survival (rwOS) from the start of the first-line therapy at time points 6, 12, 18, 24, 30, and 36 months.

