Sites of distant metastasis: visceral	
Yes	n (x.x%)
No	n (x.x%)
Disease Burden: Metastatic Sites in Liver	
Multiple lesions	n (x.x%)
No metastasis at site	n (x.x%)
Single lesion	n (x.x%)
Unknown number of lesions	n (x.x%)
Disease Burden: Metastatic Sites in Lung	
Bilateral lungs	n (x.x%)
No metastasis at site	n (x.x%)
Single lung	n (x.x%)
Unknown single bilateral status	n (x.x%)
Disease Burden: Metastatic Sites in Bone	
Multiple sites	n (x.x%)
No metastasis at site	n (x.x%)
Single site	n (x.x%)
Unknown number of sites	n (x.x%)

PFIZER CONFIDENTIAL

Table 15.16. Sites of distant metastasis at A/MBC diagnosis

Variable, n (%)	palbociclib + AI (n=xxx)
Bone (Bone only or in addition to other sites)	n (x.x%)
Bone only	n (x.x%)
Chest wall	n (x.x%)
Contralateral breast	n (x.x%)
Distant Lymph node(s)	n (x.x%)
Visceral Sites	n (x.x%)
Liver	n (x.x%)
Lung	n (x.x%)
Peritoneum	n (x.x%)
Pleural nodules	n (x.x%)
Malignant pleural effusion	n (x.x%)
Skin	n (x.x%)
Brain*	n (x.x%)
Ovary	n (x.x%)
Other: Specify	n (x.x%)
Adrenal	n (x.x%)
Bone marrow	n (x.x%)
Colon	n (x.x%)
Fallopian tubes	n (x.x%)
Omentum	n (x.x%)
Parotid gland	n (x.x%)
Soft tissue	n (x.x%)
Stomach	n (x.x%)

*Includes both brain and spinal metastasis

PFIZER CONFIDENTIAL

Table 15.1.7. Systemic Therapy, Endocrine Therapy and Sensitivity in the Adjuvant Setting

Variable, n (%)	palbociclib + AI (n=xxx)
Adjuvant Systemic Therapy	
Yes	n (x.x%)
No	n (x.x%)
Endocrine Therapy: Yes	n (x.x%)
Endocrine Sensitivity: Yes	n (x.x%)
Endocrine Sensitivity: No	n (x.x%)
Endocrine Therapy: No	n (x.x%)

Table 15.1.8. Endocrine Resistance

Variable, n (%)	palbociclib + AI (n=xxx)
Primary Endocrine Resistance	
Yes	n (x.x%)
No	n (x.x%)
Secondary Endocrine Resistance	
Yes	n (x.x%)
No	n (x.x%)

Table 15.1.9. Follow-up Times in Months

Variable	palbociclib + AI (n=xxx)
Minimum, Maximum	xx.x, xx.x
25 th percentile	xx.x
Median	xx.x
75 th percentile	xx.x

PFIZER CONFIDENTIAL

Biomarkers

Table 15.1.10. HER2, ER and PR Status

Variable, n (%)	palbociclib + AI (n=xxx)
HER2 Status	
Negative	n (x.x%)
Discordant*	n (x.x%)
ER Status	
Positive	n (x.x%)
Negative	n (x.x%)
Unequivocal	n (x.x%)
Unknown	n (x.x%)
PR Status	
Positive	n (x.x%)
Negative	n (x.x%)
Unequivocal	n (x.x%)
Unknown	n (x.x%)

*Discordant HER2 status represents patients who have ISH and IHC tests with differing results that can not be otherwise adjudicated programmatically (ie ISH = Negative and IHC = Positive)

PFIZER CONFIDENTIAL

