Breast cancer histology	List captured at initial breast cancer diagnosis including: Adenoid cystic; Cribriform; Ductal; Inflammatory; Intraductal; Lobular; Medullary with lymphoid stroma; Medullary, NOS; Mucinous; Paget's disease and infiltrating; Paget's disease and intraductal; Papillary; Secretory; Squamous cell; Tubular, and more
ECOG/KPS performance score	Score captured on date closest to (with a ± 60 day cutoff around) 1) A/MBC diagnosis; and 2) initiation of palbo
Stage at initial BC diagnosis	0, I, IA, IB, II, IIA, IIB, III, IIIA, IIIB, IIIC, IV, Unable to stage, Not found, Not applicable
Presence of distant metastasis	
Yes; No
 
Note: this variable would be "yes" if patient is diagnosed with de novo metastatic breast cancer or if patient developed metastasis after initial breast cancer diagnosis

Date of first distant metastasis	Same as initial BC diagnosis if de novo metastatic BC, otherwise captured as date that the patient developed distant metastatic disease
Site(s) of distant metastasis at MBC diagnosis	
Bone; Chest Wall; Contralateral Breast; Distant Lymph node(s); Liver; Lung; Peritoneum; Pleural nodules; Malignant pleural effusion; Skin; Brain (brain and spinal metastases); Ovary; Undocumented; Other, Specify;
 
Visceral sites (Liver, Lung, Peritoneum and Pleural nodules);

PFIZER CONFIDENTIAL

	Bone only
Comorbidities	List of comorbidities at time of A/MBC diagnosis (sourced from problem list encompassing entire patient journey and confirmed from clinician notes), including: anemia, heart arrhythmia, hypertension, myocardial infarction, congestive heart failure, peripheral vascular disease, cerebrovascular accident, hemiplegia, chronic obstructive pulmonary disease, ulcer disease, diabetes with chronic complications, diabetes without chronic complications, renal disease, connective tissue disease such as rheumatoid arthritis or lupus, Alzheimer's or other dementia, cirrhosis or other serious liver disease, non-breast cancer malignancy (excluding sites of breast cancer metastasis and malignant neoplasm of skin), metastatic solid tumor (other than breast cancer), HIV/AIDS, and other comorbidities of interest
Note: comorbidities in bold are in CCI; CCI listed in derived variables section	
Biomarkers	
ER, PR, HER2 status	Positive; Negative; Equivocal; Unknown

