Primary endocrine resistance	Relapse during first 2 years of adjuvant endocrine therapy or progressive disease within first 6 months of first-line endocrine therapy for metastatic breast cancer
Secondary endocrine resistance	Relapse while on adjuvant endocrine therapy but after first 2 years of treatment, relapse within 12 months of completing adjuvant endocrine therapy, or progressive disease 6 or more months after starting endocrine therapy for metastatic breast cancer
Charlson Comorbidity Index (CCI)	Calculated based on the presence of 17 Charlson comorbidities at A/MBC
Line of therapy	Line number (1; 2; 3; etc.) in the A/MBC setting assigned based on Syapse line of therapy algorithm
Regimen medication(s)	Systemic therapies included in line regimen defined by Syapse line of therapy algorithm
Line start date	Year, month, day
Line end date	Year, month, day
Time to first dose change	Days from palbo dose 1 start date to palbo dose 2 start date, if applicable
Number of dose changes	Number of dose reduction(s) and number of dose increases over the calendar time (quarter since February 2015) and over treatment cycle since palbo dose 1 start date

PFIZER CONFIDENTIAL

Bone only distant metastasis at MBC diagnosis	From sites of distant metastasis: bone only
Visceral distant metastasis at MBC diagnosis	From sites of distant metastasis: visceral sites Visceral sites defined as: Liver; Lung; Peritoneum; Pleural nodules; Malignant pleural effusion
Disease burden at MBC diagnosis	Lesions in liver, bone, or lung metastatic sites: Single, Multiple, Unknown
Effectiveness Outcomes	
Real-world Overall Survival (rwOS)	Length of time from the start of palbociclib + AI treatment to the earliest of the following: date of death, date of last contact, or the end of study period

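### Appendix 2 derives endocrine resistance and visceral disease differently from Sections 2.2 and 5; as written, progression on study treatment counts as a clinical characteristic

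*SAP*

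**What the plan says.** **Endocrine resistance.** Among the clinical characteristics of Objective 1a, Section 2.2 lists "documentation of endocrine sensitivity and endocrine resistance if hormone therapy was received in the adjuvant setting". Section 5 repeats this ("Documentation of endocrine sensitivity and endocrine resistance if hormone therapy received in adjuvant setting") as a sub-item of the treatment modalities received before A/MBC diagnosis.

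Section 9.2 (Appendix 2) derives endocrine sensitivity from the adjuvant setting alone. Each resistance variable there combines adjuvant relapse with a metastatic alternative:
- primary resistance: "progressive disease within first 6 months of first-line endocrine therapy for metastatic breast cancer"
- secondary resistance: "progressive disease 6 or more months after starting endocrine therapy for metastatic breast cancer"

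Section 4, inclusion criterion 4, requires that each patient "Initiated palbociclib in combination with an AI as first-line therapy after A/MBC diagnosis". The shell headed "Table 15.1.8. Endocrine Resistance" has Yes and No rows for primary and for secondary resistance, under a whole-cohort column. It states no time window and no restriction to the adjuvant setting.

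**Visceral disease.** Sections 2.2 and 5 name four sites. So does the Appendix 2 entry for sites of distant metastasis: "Visceral sites (Liver, Lung, Peritoneum and Pleural nodules". The derived variable later in the same appendix names five: "Visceral sites defined as: Liver; Lung; Peritoneum; Pleural nodules; Malignant pleural effusion".

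**The concern.** On resistance, every included patient's first-line therapy contains an AI, so first-line endocrine therapy for metastatic disease is the study treatment. Progression on it is also an rwPFS event. A table meant to describe who entered the cohort would then partly report how those patients fared, and its counts would rise with each later data cutoff. Readers who use Table 15.1.8 to judge case mix beside the rwPFS curve would be misled.

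On visceral disease, the issue is a plain definitional mismatch and has nothing to do with outcomes. Two programmers working from different sections would classify some patients differently. The result feeds the visceral row of Table 15.1.5 and the visceral row of the Cox shell (Table 15.2.1.3, repeated for the other endpoints).

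**Working it through.** **Step 1: compare the texts on resistance.**

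| Place in SAP | Setting covered |
|---|---|
| Section 2.2, Objective 1a | Adjuvant only |
| Section 5 | Adjuvant only, under treatment before A/MBC diagnosis |
| Appendix 2, endocrine sensitivity | Adjuvant only |
| Appendix 2, primary resistance | Adjuvant, or progression within 6 months on first-line metastatic endocrine therapy |
| Appendix 2, secondary resistance | Adjuvant, or progression at 6 months or later on metastatic endocrine therapy, any line |
| Table 15.1.8 | Not stated |

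With inclusion criterion 4, the primary clause is met by progression on palbociclib + AI. The secondary clause names no line, so it takes in progression on study treatment from 6 months onward and also progression on later endocrine lines. Stage IIIB/IIIC patients without metastasis fall outside both metastatic clauses. By contrast, Tables 15.1.16 to 15.1.18 are expressly limited to events before first-line therapy starts, so the SAP sets such a window where it wants one.

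**Step 2: compare the visceral lists.** Four sites (liver, lung, peritoneum, pleural nodules) against five. The only difference is malignant pleural effusion.

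**Step 3: size of the resistance problem (illustration).** The SAP states no figure to reproduce.

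From the SAP (Section 2.1): starts 03 Feb 2015 to 31 Jul 2019, assumed cutoff 01 Feb 2020, 300-400 patients. Follow-up therefore runs from 6.1 to 59.9 months. Starts are taken as uniform over the period (assumption).

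With progression hazard lp and competing hazard lo (death without progression, or loss), the probability of progression between t0 and t1 is

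lp/(lp+lo) × [exp(−(lp+lo)·t0) − exp(−(lp+lo)·t1)],

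averaged over follow-up. All rates are assumptions:
- *Upper bound:* lp = ln2/median, lo = 0, all patients metastatic.
- *Less extreme:* the median applies to rwPFS and 20% of rwPFS events are deaths, so lp = 0.8·ln2/median and lo = 0.2·ln2/median + 0.015 per month for loss. The result is multiplied by 0.90 for the metastatic share.

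Example, less extreme, median 24 months: lp = 0.0231, lo = 0.0058 + 0.015 = 0.0208, sum 0.0439. Before 6 months: 0.527 × (1 − exp(−0.263)) × 0.90 = 0.110.

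| Assumed median (months) | Upper bound: <6 mo | ≥6 mo | Total | Less extreme: <6 mo | Total |
|---|---|---|---|---|---|
| 18 | 20.6% | 46.0% | 66.6% | 14.2% | 39.6% |
| 24 | 15.9% | 41.5% | 57.4% | 11.0% | 33.5% |
| 30 | 12.9% | 37.3% | 50.3% | 8.9% | 28.9% |

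The columns before and from 6 months correspond to the primary and secondary blocks of Table 15.1.8. The totals add the two blocks.

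If only patients with adjuvant hormone therapy are scored (assumed 40-60%), the less extreme totals become 0.4 × 28.9% = 11.6% to 0.6 × 39.6% = 23.7% of all patients. That is 0.116 × 300 = 35 to 0.237 × 400 = 95 patients. Some of them already qualify through an adjuvant clause, so fewer would be newly classed as resistant.

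**Step 4: dependence on follow-up.** With a cutoff 12 months later, the upper-bound totals become 79.0/69.9/62.3% and the less extreme totals 45.4/39.2/34.3%. The increase is about 12 points and 5-6 points respectively.

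**Step 5: visceral disease.** If 2-8% of patients (assumption; the SAP gives no figure) have malignant pleural effusion and no other listed visceral site, 0.02 × 300 = 6 to 0.08 × 400 = 32 patients change group.

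**The case against.** The strongest reply is that Sections 2.2 and 5 govern. Appendix 2 does not name palbociclib + AI, its metastatic clauses may be unused parts of a general definition, and a programmer guided by Section 5 would not score on-study events. It is true that the contamination depends on how the derivation is programmed; only the conflict in wording is certain. But the adjuvant condition in Sections 2.2 and 5 limits who is documented, not which events count. A patient with adjuvant hormone therapy who progresses on study treatment still meets the Appendix 2 text, and could be endocrine-sensitive in Table 15.1.7 and resistant in Table 15.1.8.

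Other points stand in part:
- The number without adjuvant endocrine therapy already appears in Table 15.1.7, so its absence from Table 15.1.8 is a denominator problem more than a loss of information.
- Resistance is in no Cox list, Cox shell or subgroup, and the study is descriptive without hypotheses, so no effectiveness estimate changes.
- The percentages rest on assumed rates, and the effusion-only range has no anchor in the SAP.
- Malignant pleural effusion has its own row in the table of metastatic sites, so its frequency is visible under either coding, though its overlap with other sites is not.
- The italics mark the Section 2.2 text and the Appendix 2 derivations as protocol wording, so the protocol needs to be consulted.

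**Conclusion.** Both points hold as matters of text.

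For resistance, the derivation as written puts progression on study treatment into an Objective 1a characteristic, and the SAP does not say which text governs. If it is programmed literally, the share meeting a metastatic clause on first line is material: roughly 12-24% of the cohort under the narrower reading and 29-40% under the wider one, with an upper bound of 50-67%. These figures assume exponential progression with medians of 18-30 months and the other rates stated above. They exclude later-line progression, which would add to them. The conflict itself does not depend on any of these rates. The damage is confined to Table 15.1.8 and what readers infer from it.

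For visceral disease, the mismatch is smaller but reaches a model input wherever the Cox visceral covariate is fitted.

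Both should be corrected; neither affects a sample-size or power figure.

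**What to change.** **Resistance.** For Table 15.1.8, derive primary and secondary resistance only from the adjuvant clauses already in Appendix 2, counting events before the start of palbociclib + AI. Add a row for patients without adjuvant endocrine therapy so the denominator is clear. If progression before and after 6 months on first-line therapy is of interest, report it under Objective 2 as an outcome.

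**Visceral disease.** Use one site list in Sections 2.2 and 5 and in both Appendix 2 entries, and run the other list as a sensitivity coding.

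**Cost.** Two derivation entries, one table row and one site list change, with a check against the protocol wording. The data are already held. The SAP's amendment note mentions a manuscript draft, so Table 15.1.8, the visceral row of Table 15.1.5 and the Cox models containing the visceral covariate may need to be re-run.

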Variable/Statistic	palbociclib + AI (n=xxx)
Perimenopausal	n (x.x%)
Unknown	n (x.x%)
Not applicable	n (x.x%)
Region of Residence at A/MBC diagnosis, n (%)	
Northeast	n (x.x%)
Midwest	n (x.x%)
South	n (x.x%)
West	n (x.x%)

PFIZER CONFIDENTIAL

Clinical Characteristics and Comorbidities

Table 15.1.3. Clinical Characteristics and Comorbidities

Variable/Statistic	palbociclib + AI (n=xxx)
Stage at Initial Breast Cancer Diagnosis, n (%)	
Stage 0	n (x.x%)
Stage I	n (x.x%)
Stage IA	n (x.x%)
Stage IB	n (x.x%)
Stage II	n (x.x%)
Stage IIA	n (x.x%)
Stage IIB	n (x.x%)
Stage III	n (x.x%)
Stage IIIA	n (x.x%)
Stage IIIB	n (x.x%)
Stage IIIC	n (x.x%)
Stage IV	n (x.x%)
Unable to stage	n (x.x%)
Not found	n (x.x%)
Not Applicable	n (x.x%)
Histology, n (%)	
Adenoid cystic	n (x.x%)
Cribiform	n (x.x%)
Ductal	n (x.x%)
Inflammatory	n (x.x%)
Intraductal	n (x.x%)
Lobular	n (x.x%)
Medullary with lymphoid stroma	n (x.x%)
Medullary	n (x.x%)
NOS	n (x.x%)
Mucinous	n (x.x%)
Paget's disease and infiltrating	n (x.x%)
Paget's disease and intraductal	n (x.x%)
Papillary	n (x.x%)
Secretory	n (x.x%)
Squamous cell	n (x.x%)
Tubular	n (x.x%)
Performance Status at A/MBC diagnosis (ECOG Score), n (%)	
Sub-total	n (x.x%)
0	n (x.x%)
1	n (x.x%)
2	n (x.x%)
3	n (x.x%)
4	n (x.x%)
Undocumented	n (x.x%)
Total comorbidities, n (%)	
0	n (x.x%)
1	n (x.x%)
2	n (x.x%)
≥3	n (x.x%)
Charlson Comorbidity Index (CCI), n (%)	
0	n (x.x%)
1	n (x.x%)
2	n (x.x%)

PFIZER CONFIDENTIAL

Table 15.1.3. Clinical Characteristics and Comorbidities

Variable/Statistic	palbociclib + AI (n=xxx)
3	n (x.x%)
≥4	n (x.x%)
Time to Metastasis, n (%)	
≤12 months	n (x.x%)
13-24 months	n (x.x%)
25-36 months	n (x.x%)
>36 months	n (x.x%)
De novo metastatic	n (x.x%)
Disease free Interval, n (%)	
≤12 months	n (x.x%)
13-24 months	n (x.x%)
25-36 months	n (x.x%)
>36 months	n (x.x%)
De novo metastatic	n (x.x%)
Disease Free Interval (months)	
n	xx
Mean (SD)	x.x (x.xx)
Median (Q1, Q3)	x.x (x.x, x.x)
Min, Max	x.x, x.x
Metastatic Group, n (%)	
De novo	n (x.x%)
Recurrent	n (x.x%)

Table 15.1.4 Comorbidities Occurring in at Least 5% of Patients

Variable, n (%)	palbociclib + AI (n=xxx)
XXX	n (x.x%)

Comorbidities presented in descending order of frequency

PFIZER CONFIDENTIAL

Table 15.1.5. Summary of Sites of distant metastasis and disease burden at A/MBC diagnosis

Variable, n (%)	palbociclib + AI (n=xxx)
Number of distant metastatic sites	
1	n (x.x%)
2	n (x.x%)
≥3	n (x.x%)
Sites of distant metastasis: bone only	
Yes	n (x.x%)
No	n (x.x%)

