8.2 Objective 2: Effectiveness Outcomes

8.2.1 Endpoint Data

Real world Overall Survival

Table 15.2.1.19. Kaplan-Meier Analysis of rwOS from Start of 1L Using Regimen-Based Lines of Therapy

OS	palbociclib + AI (n=xxx)
No. of Events/No. of Patients	xxx/xxx
No. of Censored	xx
Minimum, Maximum	xx.x, xx.X
Kaplan-Meier Estimates in months (95% CI)	
25 th percentile	xx.x (xx.x, x,x)
Median	xx.x (xx.x, x,x)
75 th percentile	xx.x (xx.x, x,x)

Figure 15.2.1.2. Kaplan-Meier Analysis of rwOS

Table 15.2.1.3. Cox Model for Assessing Factors Associated with rwOS from Start of 1L

Parameters	Estimate	Std Error	HR	95% CI for HR	P-Value
Age in years (≥ 75 vs <50)	x.xxx	x.xxx	x.xxx	x.xxx-x.xxx	x.xxxx
Age in years (65-74 vs <50)	x.xxx	x.xxx	x.xxx	x.xxx-x.xxx	x.xxxx
Age in years (50-64 vs <50)	x.xxx	x.xxx	x.xxx	x.xxx-x.xxx	x.xxxx
Race (Black or African American vs White)	x.xxx	x.xxx	x.xxx	x.xxx-x.xxx	x.xxxx
Race (Other vs White)	x.xxx	x.xxx	x.xxx	x.xxx-x.xxx	x.xxxx
ECOG/KPS (≥ 2 vs 0)	x.xxx	x.xxx	x.xxx	x.xxx-x.xxx	x.xxxx
ECOG/ KPS (1 vs 0)	x.xxx	x.xxx	x.xxx	x.xxx-x.xxx	x.xxxx
Menopausal status (post vs pre or peri)	x.xxx	x.xxx	x.xxx	x.xxx-x.xxx	x.xxxx
Metastatic group (de novo vs recurrent)	x.xxx	x.xxx	x.xxx	x.xxx-x.xxx	x.xxxx
Stage at Diagnosis (IV vs 0 or I)	x.xxx	x.xxx	x.xxx	x.xxx-x.xxx	x.xxxx
Stage at Diagnosis (III vs 0 or I)	x.xxx	x.xxx	x.xxx	x.xxx-x.xxx	x.xxxx
Stage at Diagnosis (II vs 0 or I)	x.xxx	x.xxx	x.xxx	x.xxx-x.xxx	x.xxxx

PFIZER CONFIDENTIAL

Table 15.2.1.3. Cox Model for Assessing Factors Associated with rwOS from Start of 1L

Parameters	Estimate	Std Error	HR	95% CI for HR	P-Value
Number of disease sites (≥ 3 vs 1)	x.XXX	x.XXX	x.XXX	x.XXX-x.XXX	x.XXXX
Number of disease sites (2 vs 1)	x.XXX	x.XXX	x.XXX	x.XXX-x.XXX	x.XXXX
Time from initial diagnosis to metastasis (≤ 36 vs > 36 months)	x.XXX	x.XXX	x.XXX	x.XXX-x.XXX	x.XXXX
Visceral disease (Yes vs No)	x.XXX	x.XXX	x.XXX	x.XXX-x.XXX	x.XXXX
Prior endocrine therapy (Yes vs No)	x.XXX	x.XXX	x.XXX	x.XXX-x.XXX	x.XXXX
Prior chemotherapy (Yes vs No)	x.XXX	x.XXX	x.XXX	x.XXX-x.XXX	x.XXXX
Prior surgery (Yes vs No)	x.XXX	x.XXX	x.XXX	x.XXX-x.XXX	x.XXXX
Prior radiation therapy (Yes vs No)	x.XXX	x.XXX	x.XXX	x.XXX-x.XXX	x.XXXX

Table 15.2.1.4. Kaplan-Meier Analysis of rwOS from Start of 1L Using Regimen-Based Lines of Therapy for Patients who Received 125mg Starting Dose**Figure 15.2.1.5. Kaplan-Meier Analysis of rwOS for Patients who Received 125mg Starting Dose**

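### Metastatic-site variables are reported at A/MBC diagnosis but derived at MBC diagnosis with no cut-off at first-line start, so on-treatment spread can set baseline values and Cox covariates for stage IIIB/IIIC patients

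*SAP*

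**What the plan says.** **Who is eligible.** SAP Section 4, inclusion criterion 2, gives A/MBC as "defined as breast cancer at stage IIIB, stage IIIC, stage IV or identified as having distant metastasis". Criterion 4 then requires "Initiated palbociclib in combination with an AI as first-line therapy after A/MBC diagnosis". A patient may therefore enter at stage IIIB or IIIC with no distant metastasis. Section 5 and Table 15.1.2 list the metastatic and the A/MBC diagnosis years as separate items.

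**When the variables are reported.** Section 2.2 asks for "number and sites of distant metastasis at A/MBC diagnosis", and Section 7.2 repeats this time point. Table 15.1.5 is titled "Summary of Sites of distant metastasis and disease burden at A/MBC diagnosis" and covers number of sites, bone-only, visceral and burden. Table 15.16 (individual sites) names the same time point.

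**When the variables are captured.** Appendix 2 (Section 9.2) extracts "Site(s) of distant metastasis at MBC diagnosis" and derives "Bone only distant metastasis at MBC diagnosis", with visceral disease and disease burden at the same MBC time point. For patients who are not de novo metastatic, the date of first distant metastasis is "otherwise captured as date that the patient developed distant metastatic disease". Section 5.1 runs time to metastasis from initial to metastatic diagnosis.

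**Where they are used.** Section 7.1 lists number of disease sites (1, 2, ≥ 3), bone-only disease, visceral disease and brain metastases as candidate Cox covariates. The Cox shell, Table 15.2.1.3, has rows for number of sites, visceral disease and "Time from initial diagnosis to metastasis (≤ 36 vs > 36 months". Section 7.2 starts every time-to-event outcome at the start of first-line therapy.

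**The concern.** A baseline covariate must be known at the time origin. Take a stage IIIC patient who starts palbociclib + AI and develops liver metastases at month 14. Read literally, Appendix 2 records her as visceral, with at least one site and a time to metastasis, all from the month-14 finding. That finding is normally also her rwPFS event. An otherwise identical patient who never spreads has no site count and no time to metastasis.

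Two things are at stake. Tables 15.1.5 and 15.16 would describe as present at A/MBC diagnosis disease that appeared on treatment. In the Cox models, the affected rows would carry information from after the time origin, or the model would keep stage IIIB/IIIC patients only when they had metastasised. The rwPFS analysis by metastasis status has the same gap, because a patient with no distant metastasis is neither de novo metastatic nor recurrent metastatic.

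**Working it through.** **1. The passages side by side**

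| Variable | Reported at | Captured or derived at | Cut-off at first-line start | Level for no metastasis |
|---|---|---|---|---|
| Individual sites | A/MBC diagnosis (2.2, 7.2, Table 15.16) | MBC diagnosis (App. 2) | none | not applicable |
| Number of sites | A/MBC diagnosis (2.2, 7.2, Table 15.1.5) | from the sites above | none | none: starts at 1 in Table 15.1.5, Section 7.1 and the Cox shell |
| Bone-only, visceral | A/MBC diagnosis (Table 15.1.5) | MBC diagnosis (App. 2) | none | yes: a No row |
| Burden in liver, lung, bone | A/MBC diagnosis (Table 15.1.5) | MBC diagnosis (App. 2) | none | yes: a no-metastasis row per site |
| Time to metastasis | no A/MBC label anywhere | to metastatic diagnosis (5.1) | none | none |
| Metastatic Group | – | – | – | none: de novo or recurrent only |

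The contradiction in time point applies to the first four rows. Time to metastasis has only the missing cut-off and the missing level. Disease burden is a table variable and not a listed Cox covariate.

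**2. The plan's own figure.** The SAP states a minimum follow-up of 6 months. From 31 July 2019 to 01 February 2020 is 185 days; 185 / 30.4375 = 6.08 months, which agrees. From 03 February 2015 the maximum is 59.9 months. These two values set the censoring range below.

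**3. How many patients.** The SAP expects 300 to 400 patients and gives no IIIB/IIIC share. Assumed shares of 5% to 15% give 300 × 0.05 = 15 up to 400 × 0.15 = 60 patients. A 2% share gives 6 to 8.

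**4. Size, by simulation.** From the SAP: n = 350 (middle of 300 to 400) and censoring uniform over 6 to 60 months. Assumed: exponential rwPFS with median 20 months, 45% visceral, 70% of stage III progressions distant, the same hazard in all patients, and a true visceral hazard ratio of 1.00.

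- Hazard: λ = ln 2 / 20 = 0.0347 per month.
- Probability of an observed event: 1 − [exp(−6λ) − exp(−60λ)] / (54λ) = 1 − (0.812 − 0.125) / 1.871 = 0.63, or about 221 events.
- Share of IIIB/IIIC patients given a site count by an on-treatment metastasis: 0.63 × 0.70 = 0.44. All of these are rwPFS events.

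Results from 1,000 cohorts per setting (geometric mean hazard ratios):

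| IIIB/IIIC share | Visceral HR, never-metastatic kept as non-visceral | Visceral HR, never-metastatic dropped | Visceral HR, status fixed at first-line start |
|---|---|---|---|
| 5% | 1.03 | 1.00 | 1.00 |
| 10% | 1.06 | 0.99 | 0.99 |
| 15% | 1.10 | 1.00 | 1.00 |

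Repeat runs with other seeds, and with 80% instead of 70% distant, gave 1.02 to 1.05 at 5% and 1.07 to 1.08 at 10% in the first results column.

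When never-metastatic patients drop out, every remaining IIIB/IIIC patient has an event, visceral or not, so the visceral ratio is about right. The bias moves to stage: an indicator for IIIB/IIIC at index, true hazard ratio 1.0, is estimated at about 2.1. The Cox shell has no such row. The nearest is initial stage III against 0 or I, where the effect is diluted by patients who were initially stage III and were already metastatic at index.

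**5. If IIIB/IIIC patients progress more slowly.** With hazard ratio 0.6 for IIIB/IIIC and 80% distant, the visceral ratio at 5%, 10% and 20% is 1.08, 1.14 and 1.30 with late metastases counted. It is 1.05, 1.08 and 1.16 with status fixed at index but no separate level. A cut-off alone is therefore not enough; the no-metastasis level must also enter the model.

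**The case against.** **MBC may be loose shorthand for A/MBC.** Possibly. But Appendix 2 uses A/MBC diagnosis for age, performance status, menopausal status and comorbidities, and changes to MBC for these rows only. The SAP also lists the two diagnosis years separately. Even if the shorthand reading is right, the missing levels remain.

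**A gap between the two dates does not show post-index metastasis.** This stands. A patient diagnosed at stage IIIB may metastasise before starting palbociclib; for her the MBC date is pre-index and the more informative one. Only metastases first found after first-line start are a problem.

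**The shells do have room for non-metastatic patients.** Partly right. Table 15.1.5 has negative rows for bone-only, visceral and each organ; Appendix 2 captures presence of distant metastasis as yes or no; and Section 6 reports absent data as not documented. A reader might infer that these patients fit nowhere, which the SAP does not support. The gap is confined to number of sites, time to metastasis and Metastatic Group. Drop-out from the Cox models is an inference from those missing levels, as the SAP does not say how such patients are handled.

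**The two harms cannot be added.** Correct. Visceral inflation needs never-metastatic patients kept; selection on outcome needs them dropped. A given model shows one or the other for a given patient.

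**The effect is small and the study is descriptive.** The standard error of the log hazard ratio is about 0.136, so ratios of 1.03 and 1.10 are biases of ln(1.03)/0.136 = 0.2 and ln(1.10)/0.136 = 0.7 standard errors. Section 3 sets no hypotheses, and the Cox models depend on sample size. This limits the weight of the point but does not remove the contradiction.

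**Conclusion.** The concern holds in limited form. The SAP contradicts itself on the time point for sites, number of sites, bone-only, visceral and burden, and sets no cut-off at first-line start for these or for time to metastasis. Followed literally, Appendix 2 lets later progression define baseline values for patients who enter at stage IIIB/IIIC without metastasis. Patients already metastatic at first-line start are not exposed to this.

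The size cannot be fixed from the SAP. At assumed shares of 5% to 15%, a null visceral hazard ratio moves to roughly 1.02 to 1.10, or else the retained stage III patients are selected on outcome. With a share of a few percent, few patients are involved and the visceral bias is about 1%. These figures rest on the assumed median, visceral share and distant fraction as well as the share. They show direction and order of magnitude, and do not predict this study's bias.

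A reader might infer that time to metastasis is also mislabelled as measured at A/MBC diagnosis, or that disease burden biases the Cox models. Neither is supported. The correction should be made before analysis, but nothing here shows that the Kaplan-Meier estimates for the whole cohort are affected.

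**What to change.** 1. State one time point for these variables and use it in Sections 2.2 and 7.2, the titles of Tables 15.1.5 and 15.16, and Appendix 2.
2. Use a patient's sites, visceral, bone-only, burden and time-to-metastasis values only if the date of first distant metastasis is on or before the start of first-line palbociclib + AI. Otherwise code the patient as having no distant metastasis at index.
3. Add that level to Number of distant metastatic sites (as 0), Time to Metastasis and Metastatic Group, to the matching Cox rows, and to the rwPFS analysis by metastasis status.
4. Report the number of patients at that level, so that readers can judge the size.

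**Cost.** Wording and programming. The date of first distant metastasis and the therapy and dose 1 start dates are already listed in Appendix 2. The rule works per patient because no date per site is listed, so sites added between MBC diagnosis and first-line start cannot be recovered from the listed elements. Both conflicting wordings are italicised, which the SAP says marks protocol text, so the clarification should be recorded against the protocol as well. The statistical downside is one sparse category, which may have to be merged or left out of a model if few patients fall in it.
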